7.6 FURTHER ENDPOINTS

Time to event endpoints

Further time to event endpoints will generally be analysed in a Cox proportional hazards model similar to the primary analysis on RS. If the endpoint does not include any cause of death, a CIF plot with all-cause mortality as competing risk will be displayed; otherwise, a CIF plot with causes of death not included in the endpoint as competing risk will be displayed.

If there are less than 14 patients with events, then only descriptive statistics will be presented.

Further time to event endpoints are the following:

- Time from first to second adjudicated HHF
- Time to first all-cause hospitalisation
- Time to new onset of atrial fibrillation
- Time to adjudicated MI (fatal or non-fatal)
- Time to adjudicated stroke (fatal or non-fatal)
- Time to adjudicated TIA
- Time to first event of all-cause mortality or all cause hospitalisation
- Time to first event of adjudicated CV death or adjudicated non-fatal MI
- Time to first event of adjudicated CV death or adjudicated non-fatal stroke
- Time to first event of adjudicated CV death, adjudicated non-fatal MI or adjudicated non-fatal stroke (3-point MACE)
- Time to progression to macro albuminuria (defined as UACR >300 mg/g) from baseline for patients with baseline UACR ≤ 300 mg/g
- Time to first new onset of sustained normo- or micro albuminuria (UACR ≤ 300 mg/g) in patients with macro albuminuria at baseline
- Time to first new onset of sustained normo albuminuria (UACR < 30 mg/g) in patients with micro- or macro albuminuria at baseline
- Time to first event of composite renal endpoint¹ or adjudicated CV death
- Time to first event of composite renal endpoint¹, adjudicated CV death or adjudicated HHF
- Time to first event of composite renal endpoint¹ or all-cause mortality

- Time to first acute kidney injury (based on the preferred term)
- Time to non-cardiovascular (non-CV) death (death cases not included in the definition of adjudicated CV death)
- Time to first investigator defined CV hospitalization

¹Composite renal endpoint defined as: *chronic dialysis or renal transplant or sustained* reduction of $\geq 40\%$ eGFR (CKD-EPI)_{cr} or*

- *(for patients with eGFR (CKD-EPI)_{cr} ≥ 30 mL/min/1.73 m² at baseline): sustained eGFR < 15 mL/min/1.73m²*
- *(for patients with eGFR (CKD-EPI)_{cr} < 30 mL/min/1.73 m² at baseline): sustained eGFR < 10 mL/min/1.73 m²*

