Chronic dialysis is regarded as chronic if the frequency of dialysis is twice or more per week for at least 90 days.

*An eGFR (CDK-EPI)_{cr} reduction is considered sustained, if it is determined by two or more consecutive post-baseline central laboratory measurements separated by at least 30 days (first to last of the consecutive eGFR values). If there is no additional measurement ≥ 30 days after the eGFR reduction is observed and the patient dies within 60 days of this measurement, then the eGFR reduction is also considered sustained

Continuous endpoints:

The following endpoints will be evaluated by mixed models repeated measures (MMRM) as defined in the protocol.

- HbA_{1c} change from baseline over time (OC-AD on the randomised set and OC-OT on the treated set)
- SBP, DBP change from baseline over time (OC-AD on the randomised set and OC-OT on the treated set)
- Weight change from baseline over time (OC-AD on the randomised set and OC-OT on the treated set)
- NT-pro BNP relative change from baseline over time (OC-AD on the randomised set and OC-OT on the treated set) (value will be transformed to the log scale before MMRM analysis. Estimates obtained from the model will then be back-transformed and reported on the original scale.)
- KCCQ overall summary score change from baseline at week 52 (OC-AD on the randomised set and OC-OT on the treated set) (model will include all timepoints up to week 52)
- KCCQ individual domains change from baseline at week 52 (OC-AD on the randomised set and OC-OT on the treated set) (model will include all timepoints up to week 52)

- KCCQ total symptom score change from baseline at week 52 (OC-AD on the randomised set and OC-OT on the treated set) (model will include all timepoints up to week 52)
- KCCQ based on patient-preferred outcome change from baseline at week 52 (OC-AD on the randomised set and OC-OT on the treated set) (model will include all timepoints up to week 52)
- UACR relative change from baseline over time (OC-AD on the randomised set and OC-OT on the treated set) (value will be transformed to the log scale before MMRM analysis. Estimates obtained from the model will then be back-transformed and reported on the original scale.)
- eGFR (CKD-EPI)_{cr} change from baseline over time (OC-AD on the randomised set and OC-OT on the treated set)

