As outlined in the protocol, the above endpoints will be analysed in a mixed model with repeated measures (MMRM), including age, LVEF and eGFR (CKD-EPI)_{cr} at baseline as linear covariates and visit by treatment interaction, baseline by visit interaction, geographical region, sex and status of diabetes at baseline as fixed effects. An additional factor of “week reachable” for the parameter in question, which for each patient is the theoretically reachable planned measurement based on the time of randomisation will adjust for the different planned study times.

An unstructured covariance structure will be used to model the within-patient errors.

Descriptive statistics will be calculated for the value at visit and change from baseline based on OC-AD on the randomised set and OC-OT on the treated set.

Additionally subgroup analyses will be performed as follows:

HbA_{1c} change from baseline will be evaluated by status of diabetes (non-DM, pre-DM, DM).

NTproBNP change from baseline will be evaluated by baseline atrial fibrillation/atrial flutter (as determined by baseline ECG).

UACR will be evaluated by UACR at baseline (<30 mg/g, ≥30mg/g to ≤300mg/g, >300 mg/g).

In order to evaluate the mean effect on eGFR after approximately 3 years, the above described MMRM models will be used in the following way: a mean effect of the timepoints week 124, 148 and 172 will be calculated. Of the three timepoints, only those with at least 5 patients with a measurement at that timepoint will be included in the average calculation. This will be done for the imputations of OC-OT and OC-AD.

For MMRM subgroup analyses, the interaction term treatment-by-visit will be replaced by a treatment-by-subgroup-by-visit interaction term.

To support analysis of renal function, eGFR throughout the trial will be categorized according to the following CKD staging: All calculations for the staging of renal function will be based

on the originally measured laboratory values, not on normalised values with BI standard reference ranges.

Table 7.6: 1 CKD staging

Stage	eGFR (mL/min/1.73m ²)	Description	Label for displays	Additional labels#
1	≥90	Normal or high	≥90	≥90 (CKD 1)
2	60 to <90	Mildly decreased	60 to <90	60 to <90 (CKD 2)
3A	45 to <60	Mildly to moderately decreased	45 to <60	45 to <60 (CKD 3a)
3B	30 to <45	Moderately to severely decreased	30 to <45	30 to <45 (CKD 3b)
4	15 to <30	Severely decreased	15 to <30	15 to <30 (CKD 4)
5	<15	Kidney failure	<15	<15 (CKD 5)

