A shift table from baseline to last value on treatment for eGFR (CKD-EPI)_{cr} will be provided.

In cases where urine albumin values are reported to be below the quantification limits (e.g. <3 mg/L) the albumin / creatinine ratio is determined as missing and will not be replaced by estimated values.

Transitions from baseline to last value on-treatment based on the following UACR categories: normal (<30mg/g), microalbuminuria (30-<=300 mg/g and macroalbuminuria (>300 mg/g) will be presented.

For an evaluation of follow-up after discontinuation of trial medication an additional summary of the NT-proBNP, FG, eGFR, UACR, creatinine and the KCCQ endpoints as above will be produced. This summary will include descriptive statistics for baseline, actual values and change from baseline to last on-treatment value and follow-up, and change from last on-treatment assessment to follow-up. The TS-FU patient set will be the basis for this summary, but only those patients with a valid baseline, last value on treatment and follow-up value will be included in all displays. Analyses will be repeated for patients with at least 52 weeks of cumulative exposure (excluding treatment gaps). FG analysis will also be conducted by DM status at baseline (3 categories).

Analyses of change from baseline to LVOT and FU on the TS-FU outlined above will be additionally modelled, separately for LVOT and FU. An analysis of covariance (ANCOVA) model including treatment group, sex, geographical region and status of diabetes at baseline

as fixed effects and baseline eGFR (CKD-EPI)cr (continuous), age (continuous), LVEF (continuous) and baseline of the endpoint (if not already included) as linear covariates will be used.

In addition to the ANCOVA models described above, descriptive statistics will be presented also for creatinine for the value at visit and change from baseline based on OC-AD on the randomised set and OC-OT on the treated set.

In addition to the analyses defined above, KCCQ clinical summary score, clinical symptoms and physical limitations domain will be analysed in two responder analyses (1) defining an increase of 5 points or more from baseline as improvement and (2) defining a reduction of 5 points or more as deterioration.

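### Coding UACR as missing when urine albumin is below the quantification limit discards results known to be normal and distorts most, though not all, of the exploratory UACR analyses

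*SAP*

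**What the plan says.** The rule is in SAP Section 7.6 (Further endpoints) and reads the same in the 2017 version and the February 2021 revision. Its trigger is "In cases where urine albumin values are reported to be below the quantification limits (e.g. <3 mg/L", with 3 mg/L as an example only. Its consequence is that "the albumin / creatinine ratio is determined as missing and will not be replaced by estimated values".

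UACR is used in these places in the current version:

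- Section 7.6, mixed model on the log scale: "UACR relative change from baseline over time (OC-AD on the randomised set and OC-OT on the treated set".
- Section 7.6, strata of that model (<30, 30 to 300, >300 mg/g): "UACR will be evaluated by UACR at baseline".
- Section 7.6, shift table: "Transitions from baseline to last value on-treatment based on the following UACR categories".
- Section 7.6, time to event: "Time to first new onset of sustained normo albuminuria (UACR < 30 mg/g) in patients with micro- or macro albuminuria at baseline", a matching endpoint for patients leaving macroalbuminuria, and "Time to progression to macro albuminuria (defined as UACR >300 mg/g) from baseline for patients with baseline UACR" of at most 300 mg/g.
- Section 7.6, follow-up summary and ANCOVA on the TS-FU, which require valid baseline, last-on-treatment and follow-up values.
- Table 6.4: 1, baseline categories (demographics column only).

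Section 6.6.1 mentions multiple imputation in general terms but specifies none for UACR. Its covariate imputation covers Cox and recurrent-event models only. The SAP contains no sensitivity analysis or categorical exception for below-limit samples.

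**The concern.** A result reported as below the limit is a measurement with an upper bound. Once it is recoded as missing, the chance of being missing depends on the low value that was removed. A likelihood-based mixed model relies on data being missing at random, and that assumption does not cover this case. If treatment lowers albuminuria, more active-arm samples cross the limit and are deleted, which pulls the estimated ratio toward 1.

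The rule's evident purpose is to avoid inventing a numerical ratio. That reason does not reach the categorical analyses, because assigning such a sample to the normal category needs no invented number.

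Other parts of the SAP carry the effect further:

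- Section 6.7 takes the non-missing value nearest the planned day, so a detectable result in the same window displaces a below-limit one.
- The last value on treatment can fall back to an older, higher result.
- A patient with no usable baseline UACR has no change from baseline and leaves the model.
- Section 6.8.3 presumes that a missing laboratory baseline means the condition was absent. For the normoalbuminuria endpoint, that would treat a patient known to be normal as not normal. The SAP does not reconcile this with the endpoint's restriction to patients with micro- or macroalbuminuria.

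**Working it through.** The SAP states no share below the limit, UACR distribution or expected UACR effect, so there is no plan figure to reproduce.

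**1. Bound (from the SAP's example limit).** UACR (mg/g) = albumin (mg/L) / urine creatinine (g/L). With albumin <3 mg/L:

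| Creatinine, g/L | 0.1 | 0.2 | 0.5 | 1.0 | 2.0 |
|---|---|---|---|---|---|
| UACR below, mg/g | 30 | 15 | 6 | 3 | 1.5 |

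**2. Assumed inputs (none from the documents).** Median UACR 10, 20 or 35 mg/g. SD of log UACR 1.4 between and 0.7 within patients. Urine creatinine median 0.8 g/L, log SD 0.5. Limit 3 mg/L. Simulation of 400,000 patients per scenario, with ANCOVA of log change on treatment and baseline as a stand-in for the mixed model. Simulation error is roughly 0.005. Over 99.9% of the removed samples have a bound under 30 mg/g.

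**3. Share below the limit at baseline.** Log albumin has SD √(1.4² + 0.7² + 0.5²) = √2.70 = 1.643. The share is Φ[(ln 3 − ln(0.8 × median)) / 1.643]: Φ(−0.597) = 27.5%, Φ(−1.019) = 15.4%, Φ(−1.359) = 8.7% for medians 10, 20, 35.

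**4. Estimated treatment ratio, equal urine concentration in both arms (medians 10 / 20 / 35).**

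| True ratio | All values kept | Below-limit dropped | Half limit | Full limit |
|---|---|---|---|---|
| 1.00 | 1.006 / 1.003 / 0.999 | 1.005 / 1.002 / 0.999 | 1.005 / 1.002 / 0.999 | 1.005 / 1.002 / 1.000 |
| 0.85 | 0.854 / 0.849 / 0.851 | 0.880 / 0.869 / 0.865 | 0.875 / 0.857 / 0.855 | 0.895 / 0.873 / 0.864 |
| 0.70 | 0.700 / 0.704 / 0.700 | 0.755 / 0.742 / 0.725 | 0.743 / 0.720 / 0.706 | 0.783 / 0.749 / 0.725 |

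For a true 0.85, the share of the log effect lost by dropping is 1 − ln(0.880)/ln(0.854) = 19%, 1 − ln(0.869)/ln(0.849) = 14%, and 1 − ln(0.865)/ln(0.851) = 10%. A six-visit likelihood mixed model does not repair this: it gives about 0.86 to 0.88.

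**5. Where the bias sits (median 35, true 0.85; all values → dropped).** Baseline <30 mg/g: 0.859 → 0.889. Baseline 30 to 300: 0.849 → 0.855. Baseline >300: 0.862 → 0.862.

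**6. Baseline category <30 mg/g.** With all values, Φ[(ln 30 − ln median)/√(1.4² + 0.7²)] = 76%, 60%, 46%. Among non-missing values this becomes (75.9 − 27.5)/(100 − 27.5) = 67%, then (60.2 − 15.4)/84.6 = 53%, and (46.1 − 8.7)/91.3 = 41%. Section 7 takes percentages over all patients in the set. On that denominator the row shows 75.9 − 27.5 = 48%, 60.2 − 15.4 = 45% and 46.1 − 8.7 = 37%, with the remainder in a missing row. This ignores any earlier pre-treatment sample that could stand in.

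**7. Sustained normoalbuminuria (true 0.85, simplified to two visits), active vs placebo.** Median 10: 24.2% vs 19.0% becomes 21.0% vs 17.0%. Median 35: 12.2% vs 9.3% becomes 11.0% vs 8.5%.

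**8. Progression to >300 mg/g.** Median 10: 1.1% vs 1.6%, and median 35: 5.3% vs 7.1%. Neither changes on dropping, provided patients with missing baseline stay at risk as Section 6.8.3 says.

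**9. Dilution.** If urine on active is assumed 15% more dilute, a true 1.00 becomes 1.035 / 1.025 / 1.016 on dropping, and a true 0.85 becomes 0.910 / 0.893 / 0.880.

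**The case against.** The best defence is that the rule is explicit, avoids an arbitrary substitution value and touches only exploratory endpoints. The hierarchy in Section 7.4.1 contains the primary endpoint, recurrent HHF and eGFR slope, none of which uses UACR. Table 6.4: 1 marks UACR for demographics only. Section 7 displays a missing row where values are missing, so the gap is partly visible, although its reason is not. Some normalisation events are delayed rather than lost, because a later measurable sample below 30 mg/g can still count. All of this stands, and it limits the consequence. It does not justify discarding a category that is already known.

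A reader might infer three stronger things that the documents do not support.

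- That every UACR analysis is biased. Steps 5 and 8 show otherwise, and step 4 shows no bias in the ratio when there is no effect and urine concentration is equal. One point stays open: Section 6.8.3 does not say whether a sample whose UACR was set to missing counts as the last sampling date for censoring.
- That exactly the lowest UACR values are removed. The limit acts on albumin concentration. At creatinine 0.2 g/L, a UACR of 14 mg/g is 2.8 mg/L and is dropped. At 2.0 g/L, a UACR of 2 mg/g is 4 mg/L and is kept.
- That the error is merely conservative. It is toward no effect if the drug lowers UACR, but differing urine concentration can create a difference where none exists (step 9). Whether concentration differs between arms is an assumption. The SAP only lists increased urination as a safety topic in Section 9.7.

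**Conclusion.** The concern holds in this form. The rule turns a result known to be normal into a missing one, and nothing elsewhere in the SAP repairs it. It distorts the log-UACR model, mainly in the baseline <30 mg/g stratum, the baseline and shift categories, the last-on-treatment and TS-FU analyses, and time to sustained normoalbuminuria. The bound in step 1 is arithmetic and needs only the example limit. The size of the bias rests wholly on assumed inputs: across them, a true 0.85 is reported as about 0.86 to 0.88 and a true 0.70 as about 0.73 to 0.76. The consequence is low, because every affected endpoint is exploratory, but the change is cheap and uses data already collected.

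**What to change.** Replace the sentence in Section 7.6 with a rule along these lines:

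- A sample with albumin below the limit is classified as UACR <30 mg/g whenever the limit divided by that sample's urine creatinine is <30 mg/g. This applies to all baseline, shift and time-to-event UACR analyses, and to selection of the visit value and the last value on treatment.
- In the log-UACR models, the sample is either treated as left-censored or given half the limit divided by its observed creatinine. One method is named as the main analysis and the other as the sensitivity analysis. The full limit should not be used: in step 4 it is generally no better than dropping.
- The share of samples below the limit is reported by arm and visit.
- Section 6.8.3 states that a below-limit sample counts as a sampling date and as a non-missing baseline.

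The cost is SAP wording and a derivation step, with no new data. The downside is that a conventional substitution value or a distributional assumption is needed. Half-limit also leaves some bias when many samples fall below the limit (0.875 for a true 0.85 at the lowest assumed median). The left-censored model was not run here.

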7.7 EXTENT OF EXPOSURE

There will be three methods of calculating exposure:

- a. First intake to last intake of study drug, including off-treatment periods
- b. First intake to last intake of study drug, excluding off-treatment periods
- c. Overall observational period (randomisation until end of follow-up for vital status, see censoring for all-cause mortality in [Section 6.8.3](#))

Descriptive statistics tables with mean, standard deviation (SD), median and range of the number of days a patient was on treatment will be provided. These tables will also provide the sum-total of the time (in years) that all patients were on treatment.

Frequency tables of number and percentage of patients belonging to categorical ranges of exposure weeks will be provided as well. Following are the categories of exposure-ranges (in weeks): 0 to <12 weeks, ≥ 12 to <26 weeks, ≥ 26 to <52 weeks, ≥ 52 to <78 weeks, ≥ 78 to <104 weeks, ≥ 104 to <156 weeks, ≥ 156 weeks. Categorical ranges may be adapted based on the actual duration of the study.

7.8 SAFETY ANALYSIS

The safety analysis will be based on the treated set (TS), treatment will be evaluated as randomised.

The AE analysis will include all adverse events (including outcome events as reported by the investigator).

While tables will generally display results by randomised treatment, listings will reflect whether a measurement/AE occurred on or off treatment.

7.8.1 Adverse events

Unless otherwise specified, the analyses of adverse events will be descriptive in nature and will be based on the number of patients with AEs and not on the number of AEs.

AEs will be coded using the most recent version of the Medical Dictionary for Regulatory Activities (MedDRA) coding dictionary.

Definitions of Boehringer Ingelheim customized MedDRA Queries (BIcMQs) for new MedDRA versions are maintained by the BI dictionary maintenance group.

For analysis multiple AE occurrence data on the CRF will be collapsed into an AE provided that all of the following applies:

- All AE attributes are identical (including LLT, intensity, action taken, therapy required, seriousness, reason for seriousness, relationship, outcome, AE of special interest and also additional information of specific AEs or AESIs such as source of sepsis (urinary tract or not) or type of genital infection (fungal balanitis or vulvovaginitis versus other than fungal balanitis or vulvovaginitis)).
- The occurrences were time-overlapping or time-adjacent (time-adjacency of 2 occurrences is given if the second occurrence started on the same day or on the day after the end of the first occurrence).

For further details on summarization of AE data, please refer to [\(2\)](#), [\(12\)](#).

7.8.1.1 Assignment of AEs to treatment

The analysis of adverse events will be based on the concept of treatment emergent adverse events. That means that all adverse events occurring between first drug intake till 7 days after last drug intake will be assigned to the randomised treatment. All adverse events occurring before first drug intake will be assigned to 'pre-treatment' and all adverse events occurring after last drug intake + 7 days will be assigned to 'follow-up'.

In Section 15.3 general AE analyses tables will present only on-treatment AEs (applying the rule of 7 days for assignment as on-treatment) for the treatments groups (exceptions for urinary tract malignancies, hepatic events, lower limb amputations and bone fractures as well as adjudicated events see below). When looking at BIcMQs or standardized MedDRA queries (SMQs) and including all AEs up to completion of the trial, the time at risk for each patient will be calculated up to the individual day of trial completion (see [Section 6.8](#)).

Appendix 16.1.13.1 will include an analysis (overall summary table, frequency of AEs by system organ class (SOC) / preferred term (PT), frequency of serious adverse events (SAEs) by SOC/PT) where AEs and SAEs are assigned to the following phases: Screening, each treatment group, post-treatment for each treatment group.

The tables presenting frequency of AEs by SOC/PT and frequency of SAEs by SOC/PT will be repeated in Section 16.1.13.1 with treatment-specific post-treatment phase included, hereby also incidence rates for the post-treatment phase will be presented.

For listings, AEs will be assigned to one of the treatment phases of Screening, Placebo, Empa 10, Placebo post-treat, Empa 10 post-treat, post-study.

7.8.1.2 AE summaries

An overall summary of adverse events will be presented.

The frequency of patients with adverse events will be summarised by treatment, primary system organ class and preferred term. Incidence rates as defined in [Section 7.8.1.7](#) will generally be included. AEs will also be reported by intensity (without incidence rates). Separate tables will be provided for patients with adverse events of special interest (AESIs), for patients with serious adverse events, for patients with drug related serious AEs, for patients with fatal events, for patients with AEs leading to discontinuation, and for patients with drug-related AEs.

The frequency of patients with adverse events occurring with incidence in preferred term greater than 2% by treatment will also be presented.

Overall AE summaries, AEs by SOC and PT, SAEs and AEs leading to discontinuation will additionally be investigated by subgroups as outlined in [Table 6.4: 1](#).

Fatal AEs will be summarized up to end of the trial, also separately for those adjudicated as CV and those adjudicated non-CV cause.

The system organ classes will be sorted according to the standard sort order specified by the European Medicines Agency (EMA), preferred terms will be sorted by frequency (within system organ class).

Additionally, the following analyses will be reported in Appendix 16.1.13.1 for disclosure on EudraCT and clinicaltrials.gov:

- Frequency [N(%)] of patients with non-serious adverse events occurring with incidence in preferred term greater than 5% by treatment,
- Adverse Events per arm for disclosure on EudraCT by treatment”
- Non-serious Adverse Events for disclosure on EudraCT by treatment
- Serious Adverse Events for disclosure on EudraCT by treatment

For further details, see also [\(13\)](#).

